- e Investigational medicinal product (IMP) to be administered q2w for patients in Dose Regimen 1 and 2 Cohorts and weekly for patients in Dose Regimen 3 Cohort. Patients should be monitored for at least 30 minutes after IMP administration for any signs or symptoms of a hypersensitivity reaction. For patients who complete the extension phase, if the selected dose regimen is dosed once every other week (q2w), then the last IMP injection will occur 2 weeks before EOT; if the selected dose regimen is dosed once a week (qw), then the last IMP injection will occur 1 week before EOT. Patients will have EOT assessment at the Visit 27 (Week 156). For patients who prematurely discontinue the study treatment during the extension phase, it will be preferable to have EOT assessment 2 weeks after the last IMP injection for Dose Regimen 1 and 2 Cohort patients and 1 week after the last IMP injection for Dose Regimen 3 Cohort patients. In case the patient is unable to meet the planned schedule, the EOT visit will be used for assessment at the next protocol-defined visit after the last IMP injection. Patients will be asked to return to the site for the EOS assessment 6 weeks after the EOT visit. There will be no IMP injection at the Visit 27 (Week 156).
- f Height will be measured using stadiometer at sites during the study.
- g Juvenile Idiopathic Arthritis ACR core set (Section 9.4.1) includes: global assessment of the severity of disease by the physician, global assessment of overall well-being by the patient or parent/legal guardian, number of joints with active arthritis defined as swelling within the joint not due to deformity, OR limitation of motion with either pain or tenderness, or both, number of joints with limitation of motion, Childhood Health Assessment Questionnaire (CHAQ), hs-CRP (2.3.4). If a patient discontinues prematurely before Week 96, hs-CRP must be performed by the central laboratory at EOT.
- h Juvenile Arthritis Disease Activity Score scoring is explained in Section 9.4.2.
- i Hematology (blood should be drawn PRIOR TO drug administration): Hemoglobin, hematocrit, red blood cell (RBC) count and morphology (if RBC count is abnormal), white blood cell (WBC) differential (neutrophils, lymphocytes, monocytes, eosinophils, basophils), platelet count, absolute neutrophil count (ANC). If a patient discontinues prematurely before Week 96, the test must be performed by the central laboratory at EOT.

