11.4.3 Analyses of safety data

Safety data will be summarized descriptively. The summary of safety results will be presented by dose regimen. Further subdivision by weight group will be performed only for selected parameters given the small sample size. Additional methods including the approach to handle the dose-adjustment in safety analyses, safety analyses by time periods, and the exposure-adjusted analyses on safety events will be detailed in the statistical analysis plan.

The safety analysis will be based on the reported AEs and other safety information, such as clinical laboratory data, vital signs, etc. Safety and acceptability assessments (local tolerability) are the primary objectives of the extension parts of the studies (see [Section 9.3](#)).

All safety analyses will adhere to Sanofi “Guideline for the Analysis and Reporting of Safety Data from Clinical Trials.”

Observation period

The observation period will be divided into 5 epochs: Screening, Treatment in core period, Treatment in extension period, Follow-up, and Post-study (defined below):

- The **Screening** epoch is defined as the time from the signed informed consent date up to the time prior to the first dose of IMP.
- The **Core-treatment** epoch is defined as the time from the first dose of IMP to last dose in the core treatment phase + 13 days (or + 6 days for patients on weekly dosing), or first dose of IMP in the extension period for patients who enter the extension phase.
- The **Extension treatment** epoch is defined as the time from first dose of IMP in extension period to last dose of IMP in extension period + 13 days (or + 6 days for patients on weekly dosing). Only patients who enter the extension period have the **Extension treatment** epoch.
- The **Follow-up treatment** epoch is defined as the time from the EOT epoch (ie, the end of **core-treatment** epoch for patients not entering in the extension period; or the end of the **extension treatment** epoch for patients who enter the extension period) to last dose of IMP + 60 days.
- The **Post-study epoch** is defined as the time after the last dose of IMP + 60 days. The rationale of having “last dose of IMP + 60 days” as the end of **follow-up** epoch is to capture the events observed within approximately 5 half-lives of the last IMP.

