### Extension part

Following the 12-week core treatment period, for the dose-finding and second portions, patients who have achieved a JIA ACR30 response [REDACTED] will continue in a 144-week extension phase; for the third portion in the pcJIA study, patients will continue in an 84 week extension phase. For patients enrolled prior to the dose selection (ie, dose-finding portion), they will continue on the same dose regimen of sarilumab they were assigned to receive in the 12-week part of the study until the dose regimen is selected. Once the dose regimen is selected, patients who were not already on this dose regimen will have their doses adjusted. The dose (mg) to be administered to a patient will be calculated at baseline and will remain the same throughout the course of the 12-week core part of the study. During the extension phase, however, the patient's weight will be measured at each visit and the dose will be modified (increase only) accordingly. The dose will be capped at 150 mg for dose regimens 1 (q2w) and 3 (qw) and 200 mg (q2w) for dose regimen 2, respectively.

Patients who discontinue the study treatment prematurely will be assessed using the procedure planned for the End of Treatment (EOT) visit. These patients will be asked to return for the End of Study (EOS) assessment 6 weeks after the EOT visit. For EOT during the 12-week core part, there will be an additional PK assessment 2 weeks after the EOT visit for the dose-finding and second portions (not applicable for the third portion in pcJIA study).

The total maximum duration of participation for a patient in these studies will be 166 weeks for patients enrolled in dose-finding and second portions and up to 106 weeks for patients enrolled in the third portion (pcJIA only):

- Up to 4 weeks of screening (maximum 31 days),

- 12 weeks core treatment period,
- Up to 144 weeks extension phase for patients enrolled in dose-finding and second portions and up to 84 weeks extension phase for patients enrolled in the third portion (pcJIA only), and
- 6 weeks post-treatment follow-up.

Beside the ongoing DEC and DMC reviews of PK, PD, safety and efficacy data for futility and dose escalations, two formal interim analyses for the [REDACTED] study and three formal interim analyses for the pcJIA study will be performed. Details are provided in [Section 3](#).

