#### *Observation period*

The observation period will be divided into 5 epochs: SCREENING, TREATMENT in core period, TREATMENT in extension period, FOLLOW-UP, and POST-STUDY (defined as below):

- The SCREENING epoch is defined as the time from the signed informed consent date up to the time prior to first dose of IMP.
- The CORE TREATMENT epoch is defined as the time from first dose of IMP to last dose in core phase +13 days for patients on bi-weekly dosing or +6 days for patients on weekly dosing, or first dose of IMP in the extension period for patients who enter the extension.
- The EXTENSION TREATMENT epoch is defined as the time from first dose of IMP in extension period to last dose of IMP in extension period + 13 days for patients on bi-weekly dosing or +6 days for patients on weekly dosing. Only patients who enter the extension have the EXTENSION TREATMENT epoch.
- The FOLLOW-UP epoch is defined as the time from the end of TREATMENT epoch (ie, the end of CORE TREATMENT epoch for patients not entering in the extension period; or the end of EXTENSION TREATMENT epoch for patients who enter the extension period) to “last dose of IMP+60 days”.
- The POST-STUDY epoch is defined as the time after the “last dose of IMP+60 days”.

The entire treatment-emergent adverse event (TEAE) period includes the CORE TREATMENT, EXTENSION TREATMENT (only applicable for patients who enter the extension), and FOLLOW-UP epochs. The TEAE period for the core part includes CORE TREATMENT epoch for patients who enter the extension, and includes CORE TREATMENT and FOLLOW-UP epochs for patients not entering the extension.

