#### 2.4.5 Analyses of safety data

Safety data will be summarized descriptively for each study [REDACTED] separately. The summary of safety results will be presented by dose regimen cohort. Further subdivision by weight group will be performed only for selected parameters given the small sample size.

Safety summaries during the entire TEAE period will be provided. In addition, summaries on the important safety events will also be provided by time periods including 0-12 weeks, 0-24 weeks, and 0-52 weeks; details are provided in [Section 2.4.5.6](#). For the analyses on 0-52 weeks and entire TEAE period, summaries on the non-selected doses will only include the data collected prior to the first dose adjustment to the selected dose; a combined 'any dose' group will be added to summarize all the safety data for all treated patients. In addition, data after the dose adjustment will be summarized separately ([Section 2.4.11](#)).

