#### **2.4.5.3 Analyses of laboratory variables**

The summary statistics (including number, mean, median, SD, minimum and maximum) of all laboratory variables (laboratory values and changes from baseline) will be calculated for each visit or study assessment (baseline, each post-baseline time point, endpoint) by dose regimen cohort. This section will be organized by biological function as specified in [Section 2.1.4.4](#).

In addition, for all laboratory parameters, the mean value and mean change from baseline at each scheduled visit will be plotted by dose regimen cohort.

The incidence of PCSAs ([Appendix A](#)) at any time during the TEAE period will be summarized by biological function and dose regimen cohort whatever the baseline level and/or according to the following baseline status categories:

- Normal/missing
- Abnormal according to PCSA criterion or criteria.

For lipids, the NCEP APTIII classification will be used for the baseline.

The incidence of PCSAs at any time during the post-study period will be summarized by the actual dose regimen cohort received in the 12-week core treatment period.

The incidence of abnormal laboratory values at any time during the TEAE period will be summarized in shift tables by biological function and dose regimen cohort whatever the baseline level and/or according to the following baseline status categories:

- Normal/Missing
- Abnormal high according to the normal range
- Abnormal low according to the normal range

Listings will be provided with flags indicating the out of range values as well as the PCSA values.

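### Post-study laboratory abnormalities are tabulated by the 12-week core regimen, including for patients later switched to the selected regimen

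*SAP*

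**What the plan says.** SAP 2.4.5.3 gives post-study PCSAs their own grouping rule: their incidence "will be summarized by the actual dose regimen cohort received in the 12-week core treatment period". No other rule is given for patients who changed regimen.

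Such patients are part of the design. The SAP's description of the extension says: "Once the dose regimen is selected, patients who were not already on this dose regimen will have their doses adjusted". Table 1 of the protocol provides for this change at any visit from V13 (Week 16) to V26 (Week 144).

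The post-study epoch, in Protocol 11.4.3, "is defined as the time after the last dose of IMP + 60 days". SAP 2.1.4 uses the same limit. The clock runs from the last injection of any regimen.

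For other safety summaries, SAP 2.4.5 sets a cut. The sentence opens with "For the analyses on 0-52 weeks and entire TEAE period" and then provides that "summaries on the non-selected doses will only include the data collected prior to the first dose adjustment to the selected dose". It adds an any-dose group and sends post-adjustment data to a separate summary in Section 2.4.11. SAP 2.4.6 applies the same cut to efficacy.

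**The concern.** For a switched patient, the post-study period follows treatment with the selected regimen. The protocol chose 60 days as roughly five half-lives of the last injection, so even that injection is largely cleared by then, and the earlier regimen was stopped before it. Filing a post-study abnormality under the core regimen therefore labels it with a treatment the patient had already left, and the SAP gives no reason for doing so.

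At stake is how one descriptive table reads. For switched patients the displacement runs in one direction: a late abnormality appears in a non-selected column and not with data obtained on or after the selected regimen, which is the one the study sets out to characterize. Late laboratory values tend to come from patients being followed for a safety problem. In a sparse table, one misplaced patient is visible.

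**Working it through.** The plan states no figure for this rule. The check asks who can be mislabelled, how old the label is, and whether post-study laboratory values can exist for these patients.

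**Patients at risk.** Protocol 6.1 plans 6 evaluable patients per regimen and weight group: 6 × 3 × 2 = 36, matching its stated figure of around 36.
- If a tested regimen is selected, each weight group has 18 − 6 = 12 patients on a non-selected regimen, so 2 × 12 = 24. This also holds if the two groups are given different tested regimens.
- The protocol synopsis allows an intermediate regimen. If one is selected for both groups, all 36 are on a non-selected regimen.
- Both counts are ceilings, because in this portion only Week 12 JIA ACR30 responders enter the extension.

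**Age of the label.** Weeks from switch to the planned end-of-treatment (EOT) visit = 156 − week of switch:
- V13 (Week 16): 156 − 16 = 140 weeks, or 140/156 = 90% of treatment time.
- V20 (Week 72): 156 − 72 = 84 weeks, or 84/156 = 54%.
- V26 (Week 144): 156 − 144 = 12 weeks, or 12/156 = 8%.

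A patient who stops early after switching has fewer weeks on the selected regimen than these figures.

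**Does the safety cut reach the post-study period?** It names two analyses: 0-52 weeks and the entire TEAE period. SAP 2.1.4 defines the second: "The entire treatment-emergent adverse event (TEAE) period includes the CORE TREATMENT, EXTENSION TREATMENT (only applicable for patients who enter the extension), and FOLLOW-UP epochs". The post-study epoch is in neither, so by its wording the cut does not reach it.

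**Scheduled tests after day 60.** For q2w dosing, the protocol's extension flow chart for switched patients says "then the last IMP injection will occur 2 weeks before EOT"; for weekly dosing it is 1 week. The end-of-study (EOS) visit is 6 weeks after EOT.
- q2w: 14 + 42 = 56 days after the last dose; weekly: 7 + 42 = 49 days.
- With the EOS visit window (3 days or 1 day): 59 or 50 days, still before day 60.
- If the last injection was also given at the early edge of its own window: 62 or 51 days.

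Whichever applies, the EOS procedures in Protocol 10.1.11 include no haematology or chemistry. A switched patient who completes on schedule has no planned laboratory safety test in the post-study epoch.

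**Other sources of post-study values.**
- After early discontinuation in the extension, EOT may fall at the next protocol visit. Visits are up to 12 weeks apart, 12 × 7 = 84 days, which is past day 60. EOT includes haematology and complete chemistry (Protocol 10.1.10).
- Protocol Appendix G continues liver tests after treatment is stopped for raised ALT, on a schedule that can run past day 60.
- Protocol 9.3.1 and 10.4.2 allow follow-up of adverse events beyond the last planned visit.
- SAP 2.4.5.3 itself expects such data: it uses post-study values when assessing normalization of neutrophils and liver tests.

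The mislabelled group is therefore not empty by design, but it should be small.

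**The case against.** The strongest reply is that the rules govern different periods. The safety cut covers 0-52 weeks and the TEAE period; SAP 2.4.5.3 covers what comes after. A reader might infer that the SAP contradicts itself. The wording does not support that: the departure is from the principle behind the cut, not from its text.

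Second, post-adjustment data are assigned to Section 2.4.11 and the Appendix C table shells. Neither is visible in the public copy, so a provision for post-study values there can be neither confirmed nor excluded. That limit stands, although the explicit sentence in 2.4.5.3 still fixes the grouping of its own table.

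Third, the core label is correct for many patients with late values. Someone who stops in the first weeks of the core keeps attending to Week 12 and so has scheduled tests more than 60 days after the last dose. That patient never switched, so core regimen and last regimen are the same. This stands.

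Fourth, the post-study period lies deliberately outside the main attribution window, no hypothesis is tested, and PCSA values are flagged in listings, so single cases can be traced. This limits the consequence but does not justify the label.

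**Conclusion.** The point holds as a labelling fault in one descriptive table. Under the stated rule, any post-study PCSA in a switched patient is placed under a regimen stopped 12 to 140 weeks before the planned Week 156 EOT, and no visible text corrects this.

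Two larger readings are tempting. One is that every switched patient is misattributed. The counts of 24 and 36 are ceilings on patients at risk; only those with a laboratory test more than 60 days after the last dose can be affected. The other is that events are shifted from the selected regimen in numbers that could change a conclusion. The direction is right, but nothing in the documents indicates more than a few cases.

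The conclusion assumes 6 evaluable patients per cell and that Section 2.4.11 and Appendix C do not already handle post-study values. It concerns PCSA incidence only. No sample size or precision figure is touched.

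**What to change.** Amend the sentence in SAP 2.4.5.3 so that post-study PCSAs are summarized by the last dose regimen received, with patients adjusted to the selected regimen shown as a separate group.

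The separate group matters. Grouping by last regimen alone would pool a patient switched at Week 144, with 12 weeks on the selected regimen, with patients treated on it throughout. It would also depart from the separate handling of post-adjustment data in SAP 2.4.5 and 2.4.6. If Section 2.4.11 or Appendix C already covers this, a cross-reference is enough.

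The cost is one sentence and one extra column in one table shell. No new data are needed, and results for never-switched patients, including core discontinuations and those enrolled directly on the selected regimen, do not change.

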### ***Neutrophils***

The incidence of neutropenia will be summarized by maximal grade (lowest absolute neutrophil count reported during the TEAE period):

- Grade 1:  $\geq 1.5$  Giga/L-LLN
- Grade 2:  $\geq 1.0$  Giga/L-1.5 Giga/L
- Grade 3:  $\geq 0.5$  Giga/L-1.0 Giga/L
- Grade 4:  $< 0.5$  Giga/L

For patients with Grade 3 or 4 neutropenia, a listing with the individual neutrophil counts, WBC counts, platelet counts, lymphocytes, and hemoglobin at each visit (including re-tests taken at either central or local labs) will be provided.

The neutrophil counts at each scheduled visit during the study will be plotted by dose regimen cohort. In addition, summaries will include the following data: discontinuation, restart dosing, dosing delay, number of episodes, and normalization (to  $>1$  x LLN or return to baseline if baseline  $< LLN$ ). Laboratory measurements during the post-study period will be considered in the analysis of normalization.

### ***Thrombocytopenia***

The incidence of thrombocytopenia will be summarized by maximal grade (lowest platelet count reported during the TEAE period):

- Grade 1:  $\geq 75$  Giga/L-100 Giga/L
- Grade 2:  $\geq 50$  Giga/L-75 Giga/L
- Grade 3:  $\geq 25$  Giga/L-50 Giga/L
- Grade 4:  $< 25$  Giga/L

### ***Lymphopenia***

The incidence of lymphopenia will be summarized by maximal grade (lowest lymphocyte count reported during the TEAE period):

- Grade 1:  $\geq 0.8$  Giga/L-LLN
- Grade 2:  $\geq 0.5$  Giga/L-0.8 Giga/L
- Grade 3:  $\geq 0.2$  Giga/L-0.5 Giga/L
- Grade 4:  $< 0.2$  Giga/L

### ***Hepatic disorders***

The liver function tests (LFTs), namely AST, ALT, alkaline phosphatase, and total bilirubin, are used to assess possible drug-induced liver toxicity. The proportion of patients with PCSA values at any post-baseline visit by baseline status will be displayed by dose regimen cohort for each parameter. The proportion of patients with PCSA values at any post-baseline visit may be displayed by duration of exposure for each dose regimen cohort.

A graph of the distribution of peak values of ALT versus peak values of total bilirubin will also be presented. Note that the ALT and total bilirubin values are presented on a logarithmic scale. The graph will be divided into 4 quadrants with a vertical line corresponding to 3 x ULN for ALT and a horizontal line corresponding to 2 x ULN for total bilirubin.

The normalization (to  $< 1$  x ULN) or return to baseline (in case of baseline  $> ULN$ ) of elevated LFTs will be summarized by categories of elevation ( $> 3$  x ULN,  $> 5$  x ULN,  $> 10$  x ULN,  $> 20$  x ULN for ALT and AST;  $> 1.5$  x ULN for ALP; and  $> 1.5$  x ULN and  $> 2$  x ULN for total bilirubin) with the following categories of normalization: 1) normalized on-treatment; 2) continued into extension study (for initial analysis of 12-week core part); 3) normalized after last dose; 4) last value not normal. Laboratory measurements during the post-study period will be considered in the analysis of normalization.

Note that a patient is counted only once under the maximum elevation category.

#### **2.4.5.4 Analyses of vital sign variables**

The summary statistics (including number, mean, median, SD, minimum, and maximum) of all vital signs variables (vital signs values and changes from baseline) will be calculated for each visit or study assessment (baseline, each post-baseline time point, endpoint) by dose regimen cohort. The average of the two SBP and the two DBP readings for a patient at a particular visit will be used for analysis.

The incidence of PCSAs at any time during the TEAE period will be summarized by dose regimen cohort whatever the baseline level and/or according to the following baseline status categories:

- Normal/Missing
- Abnormal according to PCSA criterion or criteria

Listings will be provided with flags indicating the PCSA values.

#### **2.4.5.5 Analysis of anti-body/serology endpoints**

Assessment of ANA/anti-ds DNA will be summarized by visit for each dose regimen cohort, overall and by weight group.

## 2.4.6 Analyses of efficacy endpoints

Efficacy is considered as secondary in these studies, and will be summarized descriptively for each study (ie, disease type) separately.

Efficacy analyses will be done by dose regimen cohort and by weight group. Summaries on the non-selected doses will only include the data collected prior to the first dose adjustment to the selected dose. Data after the dose adjustment will be summarized separately ([Section 2.4.11](#)).

